3.2 Number of Subjects

We plan to enroll 50 subjects in each group for a total of 100 subjects.

3.3 Replacement of Subjects

Patients who drop out prior to day 100 study endpoints can be evaluated, will be replaced so that there will be 50 evaluable patients included in the study in each group.

3.4 Expected Duration of Subject Participation

3.4.1 Duration of Therapy

In the absence of graft versus host disease, treatment may continue until day 180 at the discretion of the investigator or until one of the following criteria applies:

- The investigator considers it, for safety reasons, to be in the best interest of the patient.

- General or specific changes in the patient's condition render the patient unacceptable for further treatment in the judgment of the investigator.
- Patient decision to withdraw from treatment (partial consent) or from the study (full consent),
- Pregnancy during the course of the study for a child-bearing participant
- Death
- The PI reserves the right to temporarily suspend or prematurely discontinue this study. If the rate of graft failure, which will be monitored continuously throughout the study, exceeds 11% (approximately 20% higher than what we typically expect in our prior experience) in either arm at 6 months, we will halt accrual in order to perform further analysis. Graft failure is defined as having one of the following criteria in absence of relapse:
 - Failure to reach ANC > 500/ul for 3 consecutive days in patient surviving a minimum of 28 days
 - Decrease of ANC to < 100/ul for at least 3 consecutive determinations after initial engraftment without recovery before relapse, second HCT or death
 - < 1% donor T cells as assessed by a DNA-based assay that compares the profile of amplified fragment length polymorphisms (ampFLP) or FISH studies or VNTR of the patient and donor on day +28 or beyond

The date and reason for discontinuation must be documented. Every effort should be made to complete the appropriate assessments.

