APPENDIX IV

TBI Administration

1.0 **INTRODUCTION**

1.1 **Allogeneic Hematopoietic Cell Transplant**

Allogeneic hematopoietic cell transplantation (HCT) is an effective therapy for a variety of hematologic malignancies and bone marrow failure syndromes. However, it carries a significant risk for treatment-related mortality, primarily due to infection, conditioning regimen-related toxicities, and graft versus host disease (GVHD); which continues to limit its utility. The risk of transplant-related mortality (TRM) is influenced by several factors, including patient age, disease remission status, number of prior chemotherapy regimens, co-morbid diseases, and conditioning regimen intensity. Since the 1980's, several advances have reduced the risk of TRM in patients undergoing allogeneic HCT; including more effective approaches for prevention of infection, enhancements in HLA typing and matching, and GVHD prophylactic regimens [1]. Despite this however, TRM remains high and GVHD remains a major cause of morbidity and mortality amongst allogeneic HCT patients. Even with prophylactic measures, the incidence of acute GVHD is estimated to be 40-50% among patients from HLA identical sibling donors and up to 75% in patients receiving unrelated transplants. Treatment for established GVHD can be difficult, with a mortality rate of 60-80% in patients with grades 3-4 acute GVHD. Approximately 40% of patients with acute GVHD have a durable response to corticosteroid therapy, and there has been little change in this response rate over the past 20 years despite changes to GVHD treatment regimens [2]. Thus the use of improved and effective prophylaxis is of utmost importance.

1.2 **GVHD Prophylaxis**

Currently, GVHD prophylaxis is based on a calcineurin inhibitors (cyclosporine (CsA) or tacrolimus (Tac) also called FK-506) and a short course of methotrexate (MTX). Other options include steroids, mycophenolate mofetil (MMF), and sirolimus. While the combination of Tac and MTX has largely been shown to be superior in the prevention of aGVHD compared to other regimens, toxicities from these regimens are a cause of significant morbidity after allogeneic transplant.

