2.2 Secondary Objectives

- Length of hospitalization/time to discharge
- Use of TPN (total parenteral nutrition)
- Length of time on continuous infusion narcotics
- Incidence of infection in the first 100 days post-transplantation
- Incidence of hepatotoxicity in first 100 days post-transplantation
- Incidence of nephrotoxicity in first 100 days post-transplantation
- Incidence of pulmonary toxicity in first 180 days post-transplantation
- Incidence and severity of grade II-IV and III-IV acute GVHD
- Incidence and severity of chronic GVHD
- One year relapse-free and overall survival

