3.0 STUDY DESIGN

3.1 Study Design

This is a prospective randomized trial to determine the effectiveness of different doses of GVHD prophylaxis on mucositis, engraftment and aGVHD. Study consists of two study groups of 50 subjects each.

Group A will receive Tac and MTX (15 mg/m² day +1, 10 mg/m² day +3, +6, +11).

Group B will receive Tac, Mini-dose MTX (5 mg/m² on day +1, +3, +6) and MMF.

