8.3 Reporting Procedures for All Adverse Events

All participating investigators will assess the occurrence of AEs throughout the subject's participation in the study. Subjects will be followed for toxicity for 30 days after treatment with tacrolimus or mycophenolate has been discontinued, tapered or until death, whichever occurs first. If patient continues on tacrolimus or mycophenolate for treatment of continued GVHD past the endpoint of study (1 year after infusion of HCT), adverse events will no longer be reported. The clinical course of each event will be followed until resolution, stabilization, or until it has been determined that the study treatment or participation is not the cause.

Toxicities of the blood/bone marrow, gut, liver and skin will be evaluated separately since they are likely to be affected by GVHD. GVHD severity will be determined clinically, however biopsies of affected are strongly encouraged whenever possible.

Grade 4-5 serious adverse events will be reported according to the local IRB's policies and procedures.

The investigator is responsible for ensuring that serious adverse events observed by the investigator or reported by the subject which occur after the subject has started treatment with the first study drug (day -1) are fully recorded in the subject's case report form, subject's medical records, and/or any other institutional requirement. Specific toxicities, including laboratory values and events outlined in secondary objectives will be captured per protocol; and will not necessarily be considered as part of adverse event reporting as these are expected toxicities post transplant, but may be influenced by GVHD and GVHD prevention approaches. Source documentation must be available to support all adverse events.

The investigator will provide the following for serious adverse events:

- Description of the event
- Grade of toxicity
- Attribution of relatedness to the investigational agent

In this study, descriptions and grading scales found in the NCI Common Terminology Criteria for Adverse Events (CTCAE) version 4.0 available at <http://ctep.cancer.gov> will be utilized for AE reporting.

Investigative sites will report adverse events to their respective IRB according to the local IRB's policies and procedures in reporting adverse events.

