8.5 Data Safety Toxicity Committee

It is the *Case Comprehensive Cancer Center* Principal Investigator's responsibility to ensure that ALL serious adverse events are reported to the Case Comprehensive Cancer Center's Data Safety Toxicity Committee. This submission is simultaneous with their submission to other Regulatory body.

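### The only event-based accrual pause covers graft failure; grade III-IV acute GVHD has no trigger or interim look, and the reporting sections leave it unclear whether non-fatal cases reach the safety committee

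*Combined protocol and SAP*

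**What the plan says.** **Pausing accrual.** Section 3.4.1 states "The PI reserves the right to temporarily suspend or prematurely discontinue this study", with no event, threshold or schedule attached. It then gives one numeric rule: "If the rate of graft failure, which will be monitored continuously throughout the study, exceeds 11" per cent in either arm at 6 months, accrual stops so that further analysis can be done. The threshold is described as "approximately 20% higher than what we typically expect in our prior experience". Section 14.0 plans no interim analysis. Section 13.2.5 commits the trial to the cancer center's Data and Safety Monitoring Plan, which the documents do not reproduce.

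**The risk.** Section 3.1 gives the control regimen as "Group A will receive Tac and MTX (15 mg/m² day +1, 10 mg/m² day +3, +6, +11"), and Group B as tacrolimus, 5 mg/m² of methotrexate on three days, and MMF. Section 1.1 describes established GVHD as hard to treat, "with a mortality rate of 60-80% in patients with grades 3-4 acute GVHD". Section 14.0 aims for less severe mucositis and faster engraftment without more, or more severe, acute GVHD.

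**Reporting.** Section 2.2 lists "Incidence and severity of grade II-IV and III-IV acute GVHD" as a secondary objective. Section 8.3 says that events in the secondary objectives are captured per protocol but "will not necessarily be considered as part of adverse event reporting as these are expected toxicities post transplant". Section 8.1 says that many recognized transplant toxicities are not adverse effects for this study, and that hospitalizations count as serious only if attributed to a study medication. Against that, Section 8.2.3 makes any fatal or life-threatening adverse experience serious, and Section 8.5 requires that "ALL serious adverse events are reported to the Case Comprehensive Cancer Center's Data Safety Toxicity Committee".

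**The concern.** The numeric rule watches an outcome that the plan mainly expects to improve in Group B: Section 1.2 names delayed engraftment as a methotrexate risk, and Section 14.0 hopes for earlier engraftment. The outcome that the new regimen must not worsen, acute GVHD, has no rule. Section 1.2 itself says that withheld methotrexate doses may weaken GVHD prophylaxis, and Section 1.3 concedes that mini-dose and standard-dose regimens have never been directly compared.

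If severe GVHD were more frequent in Group B, the protocol text defines no point at which accrual must pause. Nor does it require anyone to count cases by arm before the final analysis. That analysis is powered on acute GVHD of any grade by day 60, so it is neither early nor specific to the severe cases.

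**Working it through.** **1. The plan's own threshold.** If 11% is 20% above prior experience in relative terms, the implied prior graft-failure rate is 11% / 1.2 = 9.2%. The prior rate is not stated, so this cannot be checked further. No corresponding local rate is given for grade III-IV acute GVHD.

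**2. Methotrexate totals (Section 3.1).** Group A: 15 + 3 × 10 = 45 mg/m². Group B: 3 × 5 = 15 mg/m². The reduction is 30/45 = 67%, with MMF added.

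**3. The reporting sections side by side.**
- A fatal or life-threatening case that is counted as an adverse event is serious under 8.2.3 and goes to the committee under 8.5.
- The same case is a secondary-objective event, so 8.3 allows it to be left out of adverse event reporting. The wording of 8.3 is permissive and does not exclude it.
- A grade III-IV case that is neither fatal nor life-threatening has only the hospitalization or medically-important route to being serious. Section 8.1 closes the first unless a study drug is blamed; the second depends on judgment.
- No section asks for a tally of severe GVHD by arm.

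**4. Size of the risk.** The only reference rate for mini-dose methotrexate without MMF is 17% grade 3-4 (Section 1.3). The 40% below is an assumption; mortality of 60-80% is from Section 1.1; 50 patients per arm is from Section 3.2.
- At 40%: 50 × 0.40 = 20 cases, and 20 × 0.6 to 20 × 0.8 = 12 to 16 deaths.
- At 17%: 50 × 0.17 = 8.5 cases, and 5.1 to 6.8 deaths.
- Excess: 50 × (0.40 − 0.17) = 11.5 cases, and 11.5 × 0.6 to 11.5 × 0.8 = 6.9 to 9.2 deaths.

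**5. Is a useful rule feasible with 50 per arm?** At each look, take the smallest count r for which the exact binomial tail P(X ≥ r | n, 0.17) is at most 0.025:

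| Group B patients | Limit r | P(X ≥ r) at 17% | P(X ≥ r − 1) at 17% |
|---|---|---|---|
| 10 | 5 | 0.017 | 0.074 |
| 20 | 8 | 0.013 | 0.041 |
| 30 | 10 | 0.022 | 0.056 |
| 40 | 13 | 0.012 | 0.030 |

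The probability of a pause is the sum over looks of the probability of first crossing there, computed exactly:

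| True rate | 10% | 17% | 20% | 25% | 30% | 35% | 40% |
|---|---|---|---|---|---|---|---|
| P(pause) | 0.002 | 0.041 | 0.10 | 0.28 | 0.53 | 0.76 | 0.91 |

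**6. Effect on enrolment at a true 40%.** First-crossing probabilities are 0.367, 0.256, 0.219 and 0.064, leaving 0.094 with no pause. If accrual does not resume, mean Group B enrolment is 10 × 0.367 + 20 × 0.256 + 30 × 0.219 + 40 × 0.064 + 50 × 0.094 = about 23, against 50 with no rule. That assumes no delay. Grades are complete only at day 100 and the accrual rate is not given. If 5, 10 or 15 further Group B patients enter while each look matures (capped at 50), the mean is about 27, 32 or 36.

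**The case against.** Four points on the other side have weight.

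- **There are other routes to a pause.** The investigator may suspend the study at any time, and the institutional monitoring plan may add oversight. A reader might infer that nobody has to act on excess GVHD until all 100 patients are enrolled. The documents do not support this, because the monitoring plan cannot be seen. What stands is that the protocol defines no trigger, although the sponsor wrote a trial-specific one for graft failure alongside that same plan.
- **Deaths are likely to be seen.** A reader might infer that severe GVHD bypasses the committee altogether. Sections 8.2.3 and 8.5 say otherwise for fatal and life-threatening events, Section 8.3 sends grade 4-5 serious events to the IRB, and its carve-out is only permissive. What survives is the conflict between sections, and the non-fatal cases.
- **The reference rate fits poorly.** The 17% comes from small studies of four mini-doses without MMF, in matched and one-antigen-mismatched unrelated donors. Group B has three doses plus MMF and 8/8-matched related or unrelated donors. The closest cited regimen gave 5%, but after reduced-intensity conditioning. If the acceptable rate is well below 17%, the illustrative limits are too lax: a true 20% pauses only about 10% of trials. A single-arm limit also ignores the randomized control.
- **The direction of risk is open.** MMF may offset the lost methotrexate, and the plan tests non-inferiority at a hazard ratio of 1.7. A graft-failure rule is not misplaced either, since MMF is myelosuppressive (Sections 7.1.2 and 8.1.2). This argues for adding a GVHD rule beside the existing one, not for replacing it.

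**Conclusion.** The gap is real. The only event-based pause concerns graft failure, and severe acute GVHD has no defined trigger, interim look or by-arm count. Sections 8.1 and 8.3 must be reconciled with 8.2.3 and 8.5; as they stand, non-fatal grade III-IV GVHD need not reach the committee.

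The size depends on assumptions. At an assumed 40% against 17%, the excess is about 11-12 severe cases and 7-9 deaths per 50 patients, using background mortality from the literature and not a trial estimate. A reader might take the 12-16 deaths at 40% as the cost of the gap, but 5-7 of those would be expected at 17% anyway. A reader might also take the fall in enrolment from 50 to 23 as the benefit; with the wait for day-100 grades, 27-36 is more realistic if 5-15 patients enter meanwhile. The documents do not show that Group B's rate will be raised. They show that a rise would meet no pre-set rule.

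**What to change.** 1. **Section 3.4.1:** add a rule that pauses accrual and refers the trial to the Data Safety Toxicity Committee when grade III-IV acute GVHD by day 100 in Group B crosses a boundary. The statistician should set the boundary against a justified acceptable rate, preferably the center's own, and state the denominator, because Section 3.3 replaces patients who drop out before day 100. The concurrent Group A count should be shown alongside. The limits 5/10, 8/20, 10/30 and 13/40 illustrate what is achievable and are not a recommended threshold.
2. **Section 8.3:** state that grade III-IV acute GVHD is sent to the committee by arm even when it is not reported as a serious adverse event, and align 8.1 and 8.3 with 8.2.3 and 8.5.

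The cost is a short amendment and a count at a few looks. Sections 11.1.4 and 11.1.5 already have acute GVHD documented to day 100, so no new data are needed. The downside, with the illustrative limits, is about a 4% chance of an unneeded pause if the true rate is 17%. The change concerns accrual and committee review only, not the treatment of any patient.

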3.4.2 Duration of Follow Up

Patients will be followed for 1 year after T-0 (date of infusion of HCT) or until death, whichever occurs first.

The clinical course of each event will be followed until resolution, stabilization, or until it has been determined that the study treatment or participation is not the cause.

Serious adverse events that are still ongoing at the end of the study period will necessitate follow-up to determine the final outcome. Any serious adverse event that occurs after the study period and is considered to be possibly related to the study treatment or study participation will be recorded and reported immediately.

4.0 PATIENT SELECTION

Each of the criteria in the checklist that follows must be met in order for a patient to be considered eligible for this study. Use the checklist to confirm a patient's eligibility. The

checklist must be completed for each patient and must be signed and dated by the treating physician.

4.1 Inclusion Criteria

Patients must meet all of the following inclusion criteria to be eligible for enrollment

- Patients must have one of the following documented diseases:
 - Chronic Myelogenous Leukemia
 - Chronic Lymphocytic Leukemia
 - Multiple Myeloma
 - Myelodysplasia
 - Myeloproliferative disorder
 - Non-Hodgkin's Lymphoma
 - Hodgkin's Disease
 - Acute Myelogenous Leukemia
 - Acute Lymphoblastic Leukemia
 - Acute Biphenotypic Leukemia
- Patients must be undergoing a myeloablative allogeneic hematopoietic cell transplant with one of the following conditioning regimens (see APPENDIX IV for TBI administration guidelines):
 - Busulfan (≥ 12.8 mg/kg IV or PO) and cyclophosphamide (≥ 120 mg/kg)
 - Busulfan dose may be adjusted according to pharmacokinetics targeting a daily AUC of 5000 $\mu\text{mol}\cdot\text{min}/\text{L}$, per institution standard of practice.
 - TBI (≥ 1200 cGy) and Etoposide (60 mg/kg)
 - TBI (≥ 1200 cGy) and cyclophosphamide (120 mg/kg)
- Patient's disease status should meet criteria as outlined by institutional master protocol.
- Patient's donor must be a related or unrelated HLA 8/8 allele-level match (HLA-A, B, C and DRB1).
- Age 0-70
- Adult patients must have an ECOG performance status of 0 or 1. Pediatric patients must have Lansky score $\geq 60\%$
- Patients must have a life expectancy of 100 days.
- Patients must sign written informed consent.

4.2 Exclusion Criteria

- Patients who have undergone any prior transplant.
- Patients who are seropositive for human immunodeficiency virus (HIV).

- Patients with any medical illness or concurrent psychiatric illness which, in the investigators' opinion, cannot be adequately controlled with appropriate therapy.
- Patients who are pregnant or lactating.

4.3 Inclusion of Women and Minorities

Both men and women and members of all races and ethnic groups are eligible for this trial.

5.0 REGISTRATION

All subjects who have been consented are to be registered in the OnCore Database. For those subjects who are consented, but not enrolled, the reason for exclusion must be recorded.

All subjects will be registered through Cleveland Clinic and will be provided a study number by the Study Coordinator.

5.1 Randomization

Patients will be randomized 1:1 to one of the two GVHD prophylaxis regimens using blocked randomization with random block sizes. The randomization list will be generated before the start of the study by the study statistician of the study using a SAS randomization program; the list will be kept in a secured location which will only be accessible to the study coordinator. Randomization will be stratified by TBI in the preparative regimen (yes, no), donor relationship (related, unrelated), and source of hematopoietic cells (PBSC, marrow).

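### The complete randomisation list is open to the study coordinator, who also issues study numbers at registration, so upcoming assignments are not concealed from a person involved in registration

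*Combined protocol and SAP*

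**What the plan says.** On the list, Section 5.1 states: "The randomization list will be generated before the start of the study by the study statistician". On access, it states that "the list will be kept in a secured location which will only be accessible to the study coordinator". Allocation is 1:1, "using blocked randomization with random block sizes", stratified by three two-level factors: TBI in the preparative regimen, donor relationship and cell source.

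On registration, Section 5.0 states: "All subjects will be registered through Cleveland Clinic and will be provided a study number by the Study Coordinator". It also provides that "For those subjects who are consented, but not enrolled, the reason for exclusion must be recorded".

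On eligibility, Section 4.0 requires a checklist for each patient, which "must be signed and dated by the treating physician".

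The documents describe no sealed envelopes, central telephone or web allocation, pharmacy-held list or other independent holder. They also do not say that a patient's entry must be final before the next assignment can be seen.

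**The concern.** Allocation concealment means that nobody who can affect whether, when or in what order a patient enters the trial knows the next assignment. Here the only named holder of the full list also has a named part in registration. Random block sizes hinder people who try to infer the next assignment from past ones. They do nothing against someone who can read it.

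If upcoming assignments were disclosed, or if the order or timing of registration were adjusted, the arms could differ in prognosis before treatment begins. The intent-to-treat analysis in Section 14.0 would not correct that, because the imbalance would arise before randomisation takes effect. The regimens are also easy to tell apart: under Sections 6.1.2 and 6.1.3, only Group B receives MMF and only Group A has a day +11 methotrexate dose. Nothing downstream therefore masks the assignment.

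**Working it through.** The plan gives no figure on this point to reproduce. The check is a comparison of sections, followed by two calculations for context.

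**Step 1: who knows what, and when**

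| Step | Who | Source |
|---|---|---|
| Generates the full list before the study | Study statistician | 5.1 |
| Has access to the list afterwards | Study coordinator only | 5.1 |
| Issues the study number at registration | Study coordinator | 5.0 |
| Signs the eligibility checklist | Treating physician | 4.0 |
| Obtains consent | Coordinator not named for this task | 13.2.1 |
| Releases each assignment, and at what moment | Not stated | – |

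The second and third rows name the same role, and no rule separates the two tasks in time. I take the study coordinator of 5.1 and of 5.0 to be the same role.

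**Step 2: what random block sizes protect against**

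Three two-level factors give 2 × 2 × 2 = 8 strata, each with its own next assignment. A reader of the list knows all eight, so predictability for that person is 100%.

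For comparison, I simulated someone without the list who sees all past assignments and always guesses the arm that is behind in the stratum. The block sizes are not in the documents and are assumed, as are eight equally likely strata. There were 100 patients and 1:1 allocation.

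| Assumed block sizes | Correct guesses |
|---|---|
| 2, 4 | 71% |
| 2, 4, 6 | 69% |
| 4, 6 | 68% |
| 4, 6, 8 | 66% |

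Pure chance would give 50%. Random blocks limit prediction by people without the list and leave the list holder's 100% unchanged.

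**Step 3: what one exchanged pair would do**

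Inputs: 50 patients per group (Sections 3.1 and 3.2) and a target reduction in severe mucositis from 41% to 16%, which is 25 percentage points (Section 14.0). The individual risks are assumed, since the plan gives only the overall 41%.

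If one higher-risk and one lower-risk patient change places, each arm's expected rate moves by (risk difference)/50 in opposite directions:

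shift in arm difference = 2 × (risk difference)/50

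- Risks of 50% and 30%: 2 × 0.20/50 = 0.008, or 0.8 points (0.8/25 = 3.2% of the target).
- Risks of 80% and 20%: 2 × 0.60/50 = 0.024, or 2.4 points (2.4/25 = 9.6% of the target).

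Exchanging places by order of registration works only within a stratum. With 100 patients in eight strata the average is 100/8 = 12.5 per stratum, and both patients must be candidates at about the same time. Because TBI is a stratification factor, such an exchange cannot exploit risk differences due to TBI.

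**The case against.** The strongest reply is that the list is hidden from the people who matter most. The treating physician signs eligibility and, if 5.1 is followed, cannot see the list. The text does not say that the coordinator recruits, obtains consent or judges eligibility, and its wording on registration itself is passive. Selective exclusion after consent would leave a trace, because 5.0 requires reasons to be recorded. Sections 8.3 and 8.4 also refer to investigative sites with their own IRBs. If other sites enrol, a coordinator at the registering centre could serve them as a remote allocator.

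Most of this stands, and it narrows the point. A reader might infer that the coordinator controls enrolment, or that allocation is concealed from nobody. The documents support neither inference. The record of exclusions is only a partial safeguard: it shows who was left out after consent, but does not prevent foreknowledge or reveal a change in order or timing. The multi-site argument is unresolved in the documents and would not help patients enrolled where the coordinator works.

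A further objection is that unblinded mucositis grading should not be counted here. That is right. Grading by clinical staff (Section 11.1.5) is a question of assessment bias, and changing the list holder would not affect it.

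**Conclusion.** The point holds in a limited form. As written, the complete list is open to a person with a part in registration, and no step keeps the next assignment from that person until entry is final. This follows from a positive rule in 5.1, not just from missing detail. The risk is confined to disclosure by the coordinator or influence on the order or timing of registration.

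The size cannot be estimated from the documents. The range of 0.8 to 2.4 points per exchanged pair rests wholly on assumed risks. A reader might multiply the upper figure and conclude that a few exchanges, say three, would shift the result by 3 × 2.4 = 7.2 of the 25 target points. Nothing in the documents supports that number of exchanges or that risk pair; with 50% and 30%, the same three give 3 × 0.8 = 2.4 points. Nor do the documents show that any selection took place. No sample size or power figure is affected. The change is worth making because it is cheap and the arms are visibly different.

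**What to change.** Amend Section 5.1 in three respects:

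1. The list is held by someone with no part in registration. The study statistician who generates it is one option.
2. Each assignment is released singly. Sequentially numbered, opaque, sealed envelopes for each stratum would do, or electronic release if a suitable system is available. The coordinator learns only the assignment of the patient just entered.
3. Release happens only after the eligibility checklist is signed and registration is complete and irrevocable. Section 5.0 also registers consented subjects who are never enrolled, so the text should say which event commits a patient to randomisation.

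The cost is a small logistical step at each registration: someone must be available to release the assignment, or the envelopes must be prepared and accounted for. A reader might assume that OnCore can do this at no cost. Section 13.1 describes it as a data collection and trial management system with role-restricted access, but does not say that it can hold or release assignments, so this would need to be confirmed. The amendment leaves endpoints, treatments and sample size unchanged.
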